10.8 Sample Size Justification

Given that this is an initial experience with the AC system in a general use population, a sample size of a minimum of 100 patients is deemed sufficient for estimating the repositioning rate for appropriate sizing of a subsequent study. With an expected repositioning rate of 15%, a sample size of 100 patients will control the half-width of a 95% confidence interval to less than 7%.

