10.9 Analyses to be Conducted

Categorical variables will be summarized descriptively by frequencies and associated percentages. Continuous variables will be summarized descriptively by number of patients, mean, standard deviation, median, minimum, and maximum. Confidence intervals will also be provided for procedure-related variables.

Disposition of Study Patients

Patient disposition will be summarized using counts and percentages. The number and percentage of patients completed and discontinued along with the specific reasons for discontinuation will be tabulated by treatment group and in total.

Demographic and Baseline Characteristics

Summary statistics will be provided for patient demographics and pre-operative ablation characteristics.

Primary and Secondary Endpoint(s) Analyses

The number and percentage of patients requiring probe replacement/changes using the AC software prior to the initial ablation will be summarized and a 95% confidence interval for the percentage will be provided. The number and percentage of patients in whom the AC software indicates repeat ablation is indicated based on insufficient margins following the initial ablation procedure will be summarized in a similar manner.

The number and percentage of patients achieving technical success will be summarized and a 95% confidence interval will be provided. A similar summary will be provided for

technique efficacy.

The number and percentage of patients experiencing device-related and procedure-related AEs and all SAEs from the time of the first probe puncture (Visit 2) through study completion, or, if applicable, the day of early withdrawal, will be summarized by MedDRA preferred term and system organ class. Ninety-five percent confidence intervals may be provided for pre-specified adverse events of interest. The expected side effects related to MWA are as follows:

- Ascites (accumulation of fluid causing abdominal swelling)
- Biloma / bile leak (buildup of the bile within the abdomen / bile leak)
- Bile duct injury
- Bleeding requiring transfusion, embolization, or prolonged hospital stay
- Intrahepatic hematoma
- Pneumothorax or hemothorax
- Organ injury other than the liver (such as gastrointestinal injury/perforation or diaphragmatic injury/hernia)
- Fever
- General feeling of tiredness
- Infection
- Liver dysfunction
- Liver abscess
- Nausea
- Pain
- Pneumonia
- Pleural effusion

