- Post-ablation syndrome (body's response to the destroyed lesion appearing as flu-like symptoms, including fever, decreased appetite, and general discomfort occurring most typically 3 to 5 days after the ablation procedure)
- Skin burn
- Thrombosis (local coagulation or clotting of the blood in the circulatory system, with or without tube drainage)
- Tumor implantation

QOL questionnaires will be summarized with methodology consistent to the recommendations of the specific survey. Additional endpoints will be summarized with descriptive statistics.

Plans for Interim Analysis

There are no plans for interim analyses whose intent will be to stop the study early or to adapt the study design or planned number of patients.

Ongoing Review

The Sponsor will also review complications periodically, as per the Safety Management Plan.

Analysis of Safety

The analysis of safety is summarized above under Primary and Secondary Endpoint Analyses.

Handling of Dropouts or Missing Data

All analyses will be performed only on patients undergoing ablation with the AC software tool and only observed data will be analyzed. There will be no imputation of missing data for any parameters or for early terminated patients.

Multicenter Studies

No adjustment for center is planned in the statistical analysis. However, center specific analyses may be conducted pending within-center sample size to understand the effect of the performing physician's techniques and the study site's SOC may have on the overall results.

Analysis of Subgroups

No subgroup analyses are currently planned but may be considered pending the distribution of baseline demographic and clinical characteristics. Subgroup analyses, if performed, will be specified in the Statistical Analysis Plan.

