- The Per Protocol Analysis Set (PPS) will consist of all patients who are enrolled in the study and had the AC tool utilized as part of the ablation procedure with no major protocol deviations that indicate an exclusion from PPS. Lesions from patients in PPS that had the ablation procedure attempted with the AC tool will be included on the PPS. Effectiveness analyses is planned to be repeated for the PP Set. Patients followed by lesions for whom the response was “Yes” to the question “Was ablation confirmation software used to validate probe placement?” on the Ablation Confirmation form on the eCRF and had no major protocol deviations that indicate an exclusion from PPS as per the Protocol Deviation Classification document will be included on the PPS.

7 Sample Size Justification

Given that this was an initial experience with the AC system in a general use population, a sample size of a minimum of 100 patients was deemed sufficient for estimating the repositioning rate for appropriate sizing of a subsequent study. With an expected repositioning rate of 15%, a sample size of 100 patients would control the half-width of a 95% confidence interval to less than 7%. However, the study was terminated early with a smaller number of patients enrolled than planned. The reasons for early termination are difficulty in enrolling patients to the study and other studies are gathering similar data as the current study to help inform the objectives of the current study.

8 Data Safety Monitoring Board

This study did not use a DSMB.

9 Analyses to be Conducted

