9.4 Primary and Secondary Endpoints Analyses

9.4.1 Primary Endpoints Analyses

a. At the lesion level: The number of lesions that had repositioning of probe placement informed by AC software due to sub-optimal probe placement will be summarized by percentage and an exact 95% confidence interval of the percentage based on Clopper-Pearson method. Analysis will be conducted using FAS and PP analysis sets. The number of repositions informed by AC software is derived from the “Ablation Confirmation” form on the eCRF. A reposition informed by AC software is determined by an affirmative response to the question “Actions were taken due to AC software indicating probe placement was not satisfactory” and followed by choosing at least one of the three action items that are listed on the form and these lesions represent the numerator for calculating the percentage. The denominator comprises with lesions for which the following option was chosen “No actions taken despite AC software indicating probe placement was not satisfactory” along with lesions that are presented on the numerator. Lesions belong to the group “No actions taken due to AC software indicating satisfactory probe placement” are not included to the numerator or denominator.

At the patient level: The numerator is “Number of patients for whom AC suggested suboptimal probe placement for **at least one lesion** and surgeon took action.” The denominator is “Number of patients for whom AC suggested suboptimal probe placement for **at least one lesion** and surgeon took action + Number of patients for whom AC suggested suboptimal probe placement for **at least one lesion** and surgeon did not take action.” Patients who had all lesions belong to the group “No actions taken due to AC software indicating satisfactory probe placement” are not included to the numerator or denominator. An exact 95% confidence interval of the percentage will be estimated.

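### The half-width below 7% repeated in SAP 7 is not delivered by the exact interval in SAP 9.4.1 and does not describe the percentages analysed there (minor)

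*SAP*

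**What the plan says.** Protocol 10.8 plans on an expected repositioning rate of 15% and says that "a sample size of 100 patients will control the half-width of a 95% confidence interval to less than 7" percent. SAP 7 repeats this in the past conditional: "a sample size of 100 patients would control the half-width of a 95% confidence interval to less than 7" percent. Neither section names an interval method. SAP 7 then adds: "However, the study was terminated early with a smaller number of patients enrolled than planned". It gives no enrolled or treated number and no revised precision.

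The protocol's analysis is on patients: "The number and percentage of patients requiring probe replacement/changes using the AC software prior to the initial ablation will be summarized" (protocol 10.9). Under the missing-data heading of the same section, "All analyses will be performed only on patients undergoing ablation with the AC software tool". Nothing there restricts the denominator to patients flagged by AC.

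SAP 9.4.1 sets out the primary analysis. At the lesion level it prescribes an "exact 95% confidence interval of the percentage based on Clopper-Pearson method". At the patient level the text is only: "An exact 95% confidence interval of the percentage will be estimated". The denominator is the lesions (or patients with at least one lesion) for which AC indicated unsatisfactory placement, whether or not the physician acted. Cases that AC found satisfactory "are not included to the numerator or denominator". The re-ablation endpoint has the same structure.

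**The concern.** The half-width below 7% is the only precision figure in the SAP. SAP 7 gives the purpose of the estimate as sizing a later study. A reader will naturally set the figure beside the primary result. Two things then fail to match: the interval method, and the quantity being estimated. The planned quantity is a repositioning rate among treated patients. The 9.4.1 quantity is the share of AC flags that were acted on. Someone who took the second for the first, with 7 points as its design precision, would carry the wrong rate and the wrong uncertainty into the next study.

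**Working it through.** **Inputs.** Rate 15%, 100 patients, two-sided 95% (protocol 10.8, SAP 7). Exact interval and flagged-only denominator (SAP 9.4.1). The numbers treated and flagged are not in the documents. Clopper-Pearson is named only at the lesion level and is assumed here at the patient level too.

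**Step 1: reproduce the stated figure.** Wald half-width = 1.96 × √(0.15 × 0.85 / 100) = 1.96 × 0.03571 = 0.06998, or 6.998 points. Other methods at 15/100:

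| Interval | Half-width (points) |
|---|---|
| Jeffreys | 6.958 |
| Wilson | 6.989 |
| Wald | 6.998 |
| Mid-P | 7.02 |
| Agresti-Coull | 7.10 |
| Clopper-Pearson | 7.44 |
| Wald with continuity correction | 7.50 |

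The planning arithmetic is therefore right for the first three. That an approximate interval was used is inferred from this reproduction, since no method is named.

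**Step 2: apply the 9.4.1 method to the planning denominator.** Clopper-Pearson limits are the 0.025 quantile of Beta(x, n − x + 1) and the 0.975 quantile of Beta(x + 1, n − x). For x = 15 and n = 100 they are 8.65% and 23.53%. Half-width = (23.53 − 8.65) / 2 = 7.44 points, which is 0.44 above the stated limit.

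**Step 3: the number needed under the exact method.** With whole counts near 15%, 16/110 (14.5%) gives 6.998 and 17/113 (15.0%) gives 6.99. Holding the rate at exactly 15% (a fractional count in the beta quantiles), 112 patients give 7.01 and 113 give 6.98. Hence about 110 to 113.

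**Step 4: the shortfall, all-patient denominator.** Illustrations only, because the treated number is not given. At 15% observed, the exact half-widths are 8.4 points (12/80), 9.7 (9/60) and 12.1 (6/40). A lower observed rate can still come in under 7: 12/100 gives 6.83 and 7/80 gives 6.81.

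**Step 5: the 9.4.1 denominator.** Let n be the flagged count and x the number acted on. The exact half-width is smallest at x = 0 or x = n, where it equals (1 − 0.025^(1/n)) / 2.

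- n = 24: (1 − 0.8575) / 2 = 7.12 points.
- n = 25: (1 − 0.8628) / 2 = 6.86 points.

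This minimum falls as n rises, so below 25 flagged no observed result reaches 7 points. The range over every possible numerator is:

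| Flagged | Half-width (points) |
|---|---|
| 10 | 15.4 to 31.3 |
| 20 | 8.4 to 22.8 |
| 40 | 4.4 to 16.2 |

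Suppose the full 100 had been treated and 15 patients acted on, as planned. The 9.4.1 half-width would then depend on how many flags were not acted on: 10.9 points for 15/15, 20.2 for 15/20 and 18.7 for 15/30.

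**The case against.** The strongest reply is that SAP 7 is an accurate record of planning. Its wording is past conditional, a 15% rate in 100 patients already implies an all-patient base, and the very next sentence discloses that enrolment fell short. All of that stands. A reader might infer that the SAP claims the precision was achieved, or that the sample size arithmetic is wrong. The documents support neither.

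Nor does every number below 100 miss the limit. At 15% and 99 patients, Wald gives 7.03 and the exact method 7.48, but Jeffreys gives 6.993, and a lower observed rate can meet the limit under the exact method (step 4).

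It is also fair that planning with an approximate formula and analysing with an exact one is common, that 0.44 points is small, and that the study has no hypotheses. SAP 9.4.1 spells out its denominators, and the actual exact intervals will be reported. Anyone sizing a later study can work from those. This limits the harm.

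It does not remove the mismatch. The enrolment sentence tells the reader that the number of patients changed. It does not say that the interval method and the estimated quantity differ from those behind the planning figure. Whether the 9.4.1 denominator should itself be different is a separate question about the endpoint, and this point does not settle it.

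**Conclusion.** The point holds, at minor severity. The precision figure in SAP 7 is correct for an approximate interval on 100 patients, but the primary analysis in SAP 9.4.1 does not deliver it. The exact half-width at 15/100 is 7.4 points against a stated limit of 7. For the flagged-only percentages the figure does not apply at all. The method gap is small; the change of denominator is the larger part.

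The conclusion assumes Clopper-Pearson at the patient level. The half-widths at particular treated or flagged counts are illustrations. The limit of 25 flagged holds whatever the numerator. The consequence is confined to how the estimate is read and reused, and no decision rule is affected.

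**What to change.** Keep the sentence in SAP 7 as the protocol's planning statement and add after it:

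> The stated half-width is reproduced by an approximate (for example Wald) interval with all treated patients as denominator; with the exact interval of 9.4.1 it is about 7.4% at 15/100, and [value] at 15% for the number of patients actually treated. It does not apply to the percentages in 9.4.1, whose denominator is AC-flagged lesions or patients only.

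The sponsor fills in the bracketed value from the treated count. If the SAP is not reopened, the same note can go in the clinical study report. The cost is two sentences. The protocol's statement stays as it is, so no new discrepancy arises, and no further enrolment or change of analysis is proposed.

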9.1 General Conventions

Patient data will be summarized using listings and tables. All eCRF data will be listed per patient for all patients. Descriptive statistical analyses will be provided for pre-specified study endpoints. Summaries for continuous variables will include number of observations (n), mean, standard deviation, median, minimum, and maximum. Summaries for categorical variables will include number and percentage.

Analyses will be conducted using SAS software version 9.4 or higher. During the course of analysis programming of tables that are mocked up in this SAP, minor modifications may become necessary. Examples of these minor modifications include, but are not limited to, rewording of a footnote, addition of a footnote, re-labeling of a column, or addition or removal of a column from a listing. In cases where modifications to tables or listings are not related to a change in statistical analysis methodology or conclusions that could be made on the originally proposed methodology, then no amendment of the SAP is necessary. Any final analyses that

differ from what has been specified in this document will be identified within the final statistical output and documented within the clinical study report.

9.2 Disposition of Study Patients

Patient disposition will be summarized in total using counts and percentages. The number and percentage of patients completed and discontinued will be tabulated along with the specific reasons for discontinuation.

9.3 Demographic and Baseline Characteristics

Summary statistics will be provided for patient demographic, vital sign, and pre-operative characteristics. Demographic variables include age, sex, childbearing potential for female patients, ethnicity, and race. Vital sign and pre-operative characteristics include BMI, smoking status, ASA score, CEA test and CEA value, and diagnosis of hepatitis and type of hepatitis will be summarized as the pre-operative characteristics. Demographic and baseline characteristics will be listed.

Medical history will be summarized by Medical Dictionary for Regulatory Activities (MedDRA) system organ class and preferred term. Medical history, surgical history, and treatment history will be listed.

9.4 Primary and Secondary Endpoints Analyses

9.4.1 Primary Endpoints Analyses

a. At the lesion level: The number of lesions that had repositioning of probe placement informed by AC software due to sub-optimal probe placement will be summarized by percentage and an exact 95% confidence interval of the percentage based on Clopper-Pearson method. Analysis will be conducted using FAS and PP analysis sets. The number of repositions informed by AC software is derived from the “Ablation Confirmation” form on the eCRF. A reposition informed by AC software is determined by an affirmative response to the question “Actions were taken due to AC software indicating probe placement was not satisfactory” and followed by choosing at least one of the three action items that are listed on the form and these lesions represent the numerator for calculating the percentage. The denominator comprises with lesions for which the following option was chosen “No actions taken despite AC software indicating probe placement was not satisfactory” along with lesions that are presented on the numerator. Lesions belong to the group “No actions taken due to AC software indicating satisfactory probe placement” are not included to the numerator or denominator.

At the patient level: The numerator is “Number of patients for whom AC suggested suboptimal probe placement for **at least one lesion** and surgeon took action.” The denominator is “Number of patients for whom AC suggested suboptimal probe placement for **at least one lesion** and surgeon took action + Number of patients for whom AC suggested suboptimal probe placement for **at least one lesion** and surgeon did not take action.” Patients who had all lesions belong to the group “No actions taken due to AC software indicating satisfactory probe placement” are not included to the numerator or denominator. An exact 95% confidence interval of the percentage will be estimated.

b. At the lesion level: The number of lesions that had re-ablations informed by AC software due to insufficient ablation margins will be summarized by percentage and an exact 95% confidence interval of the percentage. Analysis will be conducted using FAS and PP analysis sets. The number of re-ablations informed by AC software is derived from the “Ablation Confirmation” form on the eCRF. A re-ablation informed by AC software is determined by an affirmative response to the question “Actions taken due to AC software indicating ablation margin was not complete” and followed by choosing at least one of the five action items that are listed on the form and these lesions represent the numerator for calculating the percentage. The denominator comprises with lesions for which the following option was chosen “No actions taken despite AC software indicating ablation margin was not complete” along with those presented on the numerator. Lesions belong to the group “No actions taken due to AC software indicating satisfactory margins” are not included to the numerator or denominator.

At the patient level: The numerator is “Number of patients for whom AC indicated that ablation margin was not complete for **at least one lesion** and surgeon took action.” The denominator is “Number of patients for whom AC indicated that ablation margin was not complete for **at least one lesion** and surgeon took action + Number of patients for whom no actions taken despite AC software indicating ablation margin was not complete for **at least one lesion**.” Patients who had all lesions belong to the group “No actions taken due to AC software indicating satisfactory margins” are not included to the numerator or denominator. An exact 95% confidence interval of the percentage will be estimated.

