1.0 SYNOPSIS

Full Title & Protocol Number	A Multicenter Study to Evaluate NEUWAVE Microwave Ablation System Using Ablation Confirmation in Patients with a Soft-Tissue Liver Lesion (NEU_2017_03)	
Short Title	Ablation Confirmation for soft-tissue liver lesions	
IDE / IND Number	N/A	
Sponsor	NeuWave Medical, Inc.	
Products	NEUWAVE Microwave Ablation System with Ablation Confirmation Software, 120 V, DR-000783 (Product code: NWA1US1N) The NEUWAVE Ablation Probes that may be used in this study include: LK (LK15, LK15XT, LK20, LK20XT), PR (PR15, PR20, PR15XT, PR20XT, PRS15, PRS35); and, SR (NWSR25).	
Indication	Ablation (coagulation) of soft tissue in percutaneous, open surgical, and in conjunction with laparoscopic surgical settings, including the partial or complete ablation of non-resectable liver tumors.	
Study Article Description	Ablation Confirmation (AC) Software is a computed tomography (CT) image processing software package available as an optional feature for use with the NEUWAVE Microwave Ablation System (initially marketed as Certus 140™ 2.45 GHz Ablation System). The NEUWAVE Microwave Ablation System is a general-purpose thermal ablation tool used by physicians to ablate soft-tissue lesions. In this study, the NEUWAVE Microwave Ablation System is used with NEUWAVE Ablation Probes.	
Study Design	This is a prospective, single-arm, multicenter study that will generate clinical data using the NEUWAVE Microwave Ablation System with AC software in patients undergoing microwave ablation (MWA) for soft-tissue liver lesions.	
Sample Size	N = Minimum of 100 patients treated.	
Study Population	Patients \geq 22 years old with at least one soft-tissue liver lesion.	
Geographic Area(s)	US and EMEA	
Study Duration	Enrollment: ~ 1 year	Follow-up: 6 weeks post-ablation

Procedure Description	
Patients who meet the eligibility criteria will undergo MWA of at least one soft-tissue liver lesion, in accordance with the study site's standard-of-care (SOC) for MWA. CT will be used throughout the ablation procedure for probe placement and margin assessment. Sites must use the AC software to assess optimal probe placement and to confirm complete ablation with adequate margins.
 
All ablations will be performed percutaneously. The patient will be under general anesthesia or deep conscious sedation, and antibiotics administered, if applicable, per SOC. A patient cannot have more than three lesions ablated during the procedure.

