Exclusion Criteria	
 1. Active bacterial infection or fungal infection on the day of the ablation. 2. Patients with implantable pacemakers or other electronic implants. 3. Platelet count $<$ 50,000/mm³. 4. Patients with uncorrectable coagulopathy at the time of ablation. 5. Currently breastfeeding or pregnant (latter confirmed by serum or urine pregnancy test, per site's SOC). 6. Physical or psychological condition which would impair study participation. 7. ASA (American Society of Anesthesiologists) score of \geq 4. 8. Use of hydrodissection. 9. Systemic chemotherapy or radiation therapy for the liver, within 30 days prior to the study ablation procedure. 10. INR $>$ 1.8. 11. Patient has participated in an investigational clinical study within 30 days of the screening visit for this study. 12. Patient judged unsuitable for study participation by the performing physician for any other reason.
Safety Assessments	Patients will be evaluated for device-related or procedure-related AEs and all SAEs from the time of first probe puncture (Visit 2) through study completion (Visit 3).
Statistical Analysis	Categorical variables will be summarized descriptively by frequencies and associated percentages. Continuous variables will be summarized descriptively by number of patients, mean, standard

	
deviation, median, minimum, and maximum. Confidence intervals will also be provided for procedure-related variables.
 
The number and percentage of patients requiring probe repositions based on AC prior to the initial ablation will be summarized and a 95% confidence interval for the percentage will be provided. The number and percentage of patients in whom AC indicates repeat ablation is indicated based on insufficient margins following the initial ablation procedure will be summarized in a similar manner.
 
The number and percentage of patients experiencing device-related or procedure-related AEs and any SAEs will be summarized at the preferred term level.

Interim Analysis	There are no plans for interim analyses whose intent will be to stop the study early or to adapt the study design or planned number of patients.
Schedule of Activities	See Table 1 on the next page.

Table 1: Schedule of Activities

Visit No.	Visit 1:	Visit 2			Visit 3	Unscheduled Visit
Visit	Screening ¹⁹	Ablation Day			6 Weeks	Unsched. ¹⁸
Interval Windows	≤ 60 days of Visit 2	Day 0 = ablation of target lesion			(± 3 weeks) post-ablation	NA

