5.0 STUDY OBJECTIVE

The primary objective of this study is to examine whether the feedback from the AC software impacts the performing physician's (i.e., the individual performing the ablation procedure) decision making in terms of probe(s) position or number of ablations based on insufficient ablation margins.

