5.1 Primary Endpoints

The primary endpoints supporting the study objective are, as follows:

- Percentage of repositions informed by AC due to sub-optimal probe placement.
- Percentage of re-ablations informed by AC due to insufficient ablation margins.

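### SAP 9.4.1 counts only cases with an AC warning in both primary denominators, so it estimates adherence to the software, not the rate among AC-treated patients that the study was sized for

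*SAP*

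**What the plan says.** SAP 9.4.1 builds each primary percentage from the response options on the Ablation Confirmation eCRF form. The numerator is lesions where AC found a problem and action was taken. The denominator adds only lesions where AC found a problem and no action was taken.

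- Repositioning, lesion level: "Lesions belong to the group “No actions taken due to AC software indicating satisfactory probe placement” are not included to the numerator or denominator".
- Repositioning, patient level: "Patients who had all lesions belong to the group “No actions taken due to AC software indicating satisfactory probe placement” are not included" in either term.
- Re-ablation, lesion level: "Lesions belong to the group “No actions taken due to AC software indicating satisfactory margins” are not included to the numerator or denominator".
- Re-ablation, patient level: the only term added to the acted-on count is the "Number of patients for whom no actions taken despite AC software indicating ablation margin was not complete for" at least one lesion.

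The protocol reads differently. Section 5.1 lists endpoints such as "Percentage of re-ablations informed by AC due to insufficient ablation margins" and names no denominator. The Synopsis analysis text says "The number and percentage of patients requiring probe repositions based on AC prior to the initial ablation will be summarized", and section 10.9 repeats this with slightly different wording. For margins, both places call for the percentage of patients in whom AC indicates a repeat ablation. Section 10.5 assesses the objective by recording whether AC feedback indicates repositioning or repeat ablation.

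Section 10.8 justifies the sample size by an expected repositioning rate of 15% and a 95% CI half-width below 7% with 100 patients. The Synopsis describes those patients as "N = Minimum of 100 patients treated", and section 6.2 adds that AC must have been used. SAP section 7 repeats the justification and the aim of estimating the repositioning rate to size a later study.

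**The concern.** The SAP ratio is the probability of action given an AC warning. The frequency of warnings drops out of it, because every case in the denominator has one. The ratio therefore cannot show how often AC changes a procedure, and it cannot supply the repositioning rate that protocol 10.8 and SAP section 7 name as the purpose of the estimate.

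For re-ablation the mismatch is sharper. The protocol's analysis text asks for the percentage of patients in whom AC indicates repeat ablation. Within the SAP denominator that percentage is 100% by construction.

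The study is descriptive and tests nothing, so the point estimate and its interval are the whole primary result. A reader who takes a high adherence figure as the percentage of procedures that AC altered could overstate the effect several-fold.

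**Working it through.** **Notation.** Count each patient once. Let A = patients with an AC warning that was acted on, I = patients with a warning and no action, S = patients whose lesions AC found satisfactory throughout.

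- SAP 9.4.1: A / (A + I)
- All-patient, AC-informed action: A / (A + I + S)
- All-patient, AC-indicated: (A + I) / (A + I + S)

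**Inputs.** Rate 15%, n = 100, half-width below 7 points (protocol 10.8); 95% Clopper-Pearson intervals (SAP 9.4.1). The documents give neither the number of ignored warnings nor the final sample size, so all other counts below are assumptions.

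**Step 1: the plan's own figure.** The Wald half-width is 1.96 × √(0.15 × 0.85 / n).

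- n = 100: 6.998 points
- n = 99: 7.03 points

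Wilson at 15/100 gives 6.99. The statement holds, but only just, and only if all 100 treated patients form the denominator. The SAP's exact method gives 8.65 to 23.53% for 15/100, a half-width of (23.53 − 8.65)/2 = 7.44 points, already above 7.

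**Step 2: the same 15 acted-on patients under each rule.**

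| Ignored warnings (assumed) | SAP ratio | Exact 95% CI | All-patient rate, N = 100 |
|---|---|---|---|
| 0 | 15/15 = 100% | 78.2 to 100% | 15.0% (8.65 to 23.53%) |
| 4 | 15/19 = 78.9% | 54.4 to 93.9% | 15.0% |
| 15 | 15/30 = 50.0% | 31.3 to 68.7% | 15.0% |

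The protocol quantity does not move, while the SAP figure halves. Across 15 to 30 warned patients the exact half-width of the SAP ratio is about 11 to 20 points, so the below-7 statement in SAP section 7 does not describe it.

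**Step 3: the converse.** One SAP result fits very different rates.

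- 15/15 = 100% is compatible with 15/40 = 37.5% (22.7 to 54.2%) and with 15/100 = 15.0%.
- With 80% adherence assumed, the SAP gives 80% whether 10, 20 or 60 of 100 patients had a warning. The all-patient rates are 8%, 16% and 48%.

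**Step 4: re-ablation.** Suppose 100 patients, 50 with a margin warning, 20 acted on.

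- SAP ratio: 20/50 = 40.0% (26.4 to 54.8%)
- AC-informed action: 20/100 = 20.0% (12.7 to 29.2%)
- AC-indicated: 50/100 = 50.0% (39.8 to 60.2%)

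The last is the quantity in protocol 10.9, and the SAP primary analysis does not report it.

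**Step 5: early termination.** SAP section 7 says fewer patients were enrolled than planned. At 15% and assumed N of 40, 60 and 80 (6/40, 9/60, 12/80), the exact half-widths for the all-patient rate are 12.1, 9.7 and 8.4 points.

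**The case against.** The strongest reply is that protocol 5.1 names no denominator and that the objective in section 5.0 is to "examine whether the feedback from the AC software impacts the performing" physician's decisions. Action given a warning bears directly on that, so the SAP could be said to fill a gap rather than contradict a definition. It is true that the protocol nowhere writes out the all-patient denominator. Its Full Analysis Set definition and its missing-data rule also say who is analysed rather than what a percentage is divided by, so they are weak support alone. The sample-size statement speaks only to repositioning. But the Synopsis and sections 10.5, 10.8 and 10.9 together point one way, and nothing in the protocol restricts either percentage to patients with a warning.

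SAP 9.6 does plan a descriptive summary of repositioning, and SAP 9.1 lists all eCRF data. That summary is not specific to AC and carries no interval, and a listing is not a pre-specified estimate. SAP 9.1 mentions mock-up tables that are not in the text available here. They might show the satisfactory counts, but they would not change the denominators that 9.4.1 states.

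The study tests no hypothesis, and it stopped partly because other studies gather similar data. This weakens the sizing purpose, but SAP section 7 still states that purpose. The SAP is also open about its ratio, so a careful reader could see what it is. That does not supply the missing estimate.

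**Conclusion.** The concern holds. Both primary percentages, at lesion and patient level, estimate adherence to AC warnings. The rate that the study was sized to estimate has no pre-specified AC-specific analysis with a confidence interval in the SAP text. In the planning case the reported figure could lie anywhere from 50% to 100% where the all-patient rate is 15.0%. That range assumes 0 to 15 ignored warnings; the 15% and n = 100 are the protocol's own.

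The effect is on what the primary estimate means, not on any test, and no data are lost. Because estimation is the study's only purpose, the definition should be corrected and not merely annotated.

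Two linked points remain open. First, the protocol moves between AC-informed action (5.1) and AC indication (10.5, and 10.9 for re-ablation), and the SAP adopts action without comment. Second, a patient with one warning acted on and another not fits both terms of the patient-level denominator and could be counted twice.

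**What to change.** 1. Make the primary denominator all Full Analysis Set patients, and in parallel all Full Analysis Set lesions, in which AC assessed placement (repositioning) or margins (re-ablation). Include the satisfactory group and give exact 95% intervals. For repositioning this is the Full Analysis Set itself, since SAP section 6 admits only cases where AC was used to validate placement. For re-ablation use the field on AC use for margin assessment, listed in SAP 9.6.
2. For repositioning, report AC-informed probe changes with the AC-indicated count beside them. For re-ablation, report both AC-informed action and AC-indicated repeat ablation over the same denominator. The sponsor should state which numerator is primary.
3. Keep the present ratio as a secondary measure labelled as adherence to AC feedback.
4. State the precision attained at the actual sample size, by the exact method, in place of the carried-over below-7 statement.
5. Say that each patient is counted once, and how a patient with both acted-on and not-acted-on warnings is classified.

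The cost is SAP wording and revised tables: two endpoints, two levels, the Full Analysis and Per Protocol sets, and the SAP 9.10 subgroup tables. No new data are needed. With each patient counted once, the all-patient percentages based on action cannot exceed the adherence ratio; the AC-indicated percentage may be higher or lower than it.
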